## 2.8 Pharmacokinetic endpoints

The PK analysis set will be used for the pharmacokinetics analyses.

PK parameters in [Table 2-5](#) will be determined using the actual recorded sampling times and non-compartmental method(s) with Phoenix WinNonlin (Version 6.4 or higher). If  $R_{sq\_adj} < 0.75$  or  $AUC\%_{Extrap} > 20\%$ , then  $\lambda_z$ ,  $T_{1/2}$ ,  $AUC_{inf}$ ,  $V_z/F$ ,  $CL/F$  will be flagged for exclusion.

Drug concentrations below the lower limit of quantitation (LLOQ) will be set to zero by the Bioanalyst and will be displayed in the listings as zero and flagged. Below LLOQ values will be treated as missing for the calculation of the geometric means and geometric CV%, and as zero for all other calculations including calculation of PK parameters.

CCI

AUClast	The AUC from time zero to the last measurable concentration sampling time (tlast) (mass x time x volume  )
AUCinf	The AUC from time zero to infinity (mass x time x volume  )
Cmax	The maximum (peak) observed plasma, blood, serum, or other body fluid drug concentration after single dose administration (mass x volume  )
Tmax	The time to reach maximum (peak) plasma, blood, serum, or other body fluid drug concentration after single dose administration (time)
Lambda_z	Smallest (slowest) disposition (hybrid) rate constant (time  ) may also be used for terminal elimination rate constant (time  )
T1/2	The elimination half-life associated with the terminal slope (λz) of a semi logarithmic concentration-time curve (time). Use qualifier for other half-lives
CL/F	The total body clearance of drug from the plasma (volume x time  )
Vz/F	The apparent volume of distribution during terminal phase (associated with λz) (volume)

[illegible][illegible]

CCI

CCI

CCI

- PK parameters with efficacy outcomes CCI related to parasite dynamics, cure, and protein levels CCI wherever applicable

See [Section 2.9](#).

- Presence of gametocytes at baseline (pre-dose) and post-treatment, respectively

Number and percent of patients with gametocytemia and descriptive summaries at each post-baseline time (2, 4, 6, 8, 12 hours during visit 1, etc.) and during the 28 days post-baseline period will be provided by baseline status of gametocytemia (present, absent, missing). Summaries will be presented using local labs. Any data collected from bioanalytical lab (based on PCR, i.e. baseline, 168h, 360h, EOS) may be summarized in an addendum.

NOTE: The following endpoints, if analyzed, will be done outside the CSR:

- IC50 of parasites isolates before and after treatment (recrudescence infections) by *in vitro* growth inhibition assays
- CCI
- Genetic data (e.g., polymorphisms)

## 2.11 Interim analysis

CCI

CCI

### 3 Sample size calculation

#### 3.1 Part A

CCI

CCI

CCI

CCI

### 3.2.1 B1 – INE963 and KAE609 (cipargamin) combination

CCI

CCI

CCI

CCI

The probability to meet the dual non-inferiority criteria for Part B is greater than 89% if SoC cure rate is more than 90%, when the true difference ( $\delta$  = SoC cure rate - combination cure rate) is zero. Assuming the true SoC cure rate is 98% and the true difference is 0.05, the probability is 95% to meet the dual non-inferiority criteria as shown in [Table 3-5](#).

**Table 3-5 Power to declare non-inferiority to SoC for different scenarios**

True SoC cure rate	SoC : (KLU + cipargamin) = 30 : 30			
	$\delta=0$	$\delta=0.05$	$\delta=0.1$	$\delta=0.2$
0.85	0.78	0.55	0.34	0.09
0.90	0.89	0.67	0.40	0.09
0.95	0.99	0.84	0.56	0.12
0.98	1.00	0.95	0.71	0.18

KAF156 and lumefantrine-SDF co-administered in a loose combination were assessed in fasted condition in patients down to 2 years of age in a Phase 2b dose finding study (CKAF156A2202). The positive benefit-risk balance supports the evaluation of the identified effective and safe dose (400mg of KAF156 and 480 mg of lumefantrine SDF) of the fixed-dose combination of KAF156 and LUM-SDF, i.e., KLU156 in combination with 75 mg KAE609 to explore possibility of a single dose cure in uncomplicated *P. falciparum* malaria.

Data available for KLU156 as a combination from completed clinical study are summarized in [Table 3-6](#). The dose selected for this combination is KAF156 400 mg and 480 mg of lumefantrine SD using fed conditions, therefore only data from KAF156 of 400 and

lumefantrine 960 mg SD (fasting conditions) was used to derive the MAP prior for patients  $\geq 12$  years of age. The expected food effect is approximately two-fold.

### 3.2.3 C2 – KLU156 and cipargamin in combination

In Cohort C2, approximately 120 evaluable patients infected with *P. falciparum* will be randomized to KLU156+cipargamin vs SoC (Coartem) at a 2:1 ratio (80 evaluable patients treated with KLU156+cipargamin combination vs 40 evaluable patients treated with SoC). The sample size derivation is based on Bayesian analysis using informative priors for the SoC based on data from patients  $< 12$  years.

The probability to meet the dual non-inferiority criteria for Part C is greater than 91% if SoC cure rate is more than 95%, when the true difference ( $\delta$  = SoC cure rate - combination cure rate) is zero. Assuming the true SoC cure rate is 98% and the true difference is 0.03, the probability is 85% to meet the dual non-inferiority criteria as shown in [Table 3-5](#).

**Table 3-7 Power to declare non-inferiority to SoC for different scenarios**

True SoC cure rate	SoC : (KLU + cipargamin) = 40 : 80					
	$\delta=0$	$\delta=0.01$	$\delta=0.03$	$\delta=0.05$	$\delta=0.1$	$\delta=0.15$
0.85	0.60	0.54	0.43	0.33	0.14	0.05
0.90	0.65	0.58	0.43	0.31	0.11	0.03
0.95	0.91	0.82	0.60	0.38	0.08	0.01
0.98	1.00	0.98	0.85	0.61	0.12	0.01

## Secondary endpoints(s)

CCI

For Parts B & C, no formal comparison is planned between the combination therapy and SoC based on PCT.

CCI

## 4 Change to protocol specified analyses

CCI

## 5 Appendix

### 5.1 Imputation rules

#### 5.1.1 AE date imputation

A missing AE start date will be imputed using the logic matrix described in [Table 5-1](#).

**Table 5-1 Imputation rules for a partially missing AE start date**

	AEM missing	AEM<TRTM	AEM=TRTM	AEM>TRTM
AEY missing	Not imputation	Not imputation	Not imputation	Not imputation
AEY<TRTY	(D)	(C)	(C)	(C)
AEY=TRTY	(B)	(C)	(B)	(A)
AEY>TRTY	(E)	(A)	(A)	(A)

AEM=Month AE started, AEY=Year AE started

TRTM=Month treatment started, TRTY=Year treatment started

Table 5-2 is the legend to the logic matrix shown in Table 5-1 and details the relationship of AE start date to study treatment start date.

**Table 5-2 Imputation legend and AE/treatment start date relationship**

AE start date relationship	Imputation
(A) After treatment start or uncertain	MAX(01MMMYYYY, TRTSDT+1)
(B) Uncertain	TRTSDT+1
(C) Before treatment start	15MMMYYYY
(D) Before treatment start	01JULYYYY
(E) After treatment start	01JANYYYY

Before treatment start: Partial date indicates AE start date is prior to treatment start date.

After treatment start: Partial date indicates AE start date is after treatment start date.

Uncertain: Partial date insufficient to determine relationship of AE start date to treatment start date.

All events with start date before or on the cut-off date and end date after the cut-off date will be reported as 'ongoing'. The same rule will be applied to AEs starting before or on the cut-off date and not having documented end date.

No imputation will be performed for missing/incomplete AE end dates.

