## 2.7 Safety analyses

For all safety analyses, the Safety set will be used. Safety summaries include data from the on-treatment period with the exception of baseline data which will be summarized where appropriate (e.g., change from baseline summaries). In particular, summary tables for AEs will summarize treatment-emergent AEs (i.e. with a start date on or after the first treatment).

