#### 2.7.1.1 EudraCT and clinicaltrials.gov requirements

For legal requirements of clinicaltrials.gov and EudraCT, two on-treatment tables are required:

- On-treatment deaths resulting from SAEs suspected to be study drug related and SAEs regardless of study drug relationship by SOC and PT
- Non-serious AEs regardless of study drug relationship, with an incidence rate greater than 5% by SOC and PT

These summaries will include any events starting or worsening in the on-treatment period.

If for the same patient, if several consecutive AEs (irrespective of study treatment causality, seriousness, and severity) occurred with the same SOC and PT:

- a single occurrence will be counted if there is  $\leq 1$  day gap between the end date of the preceding AE and the start date of the consecutive AE
- more than one occurrence will be counted if there is  $> 1$  day gap between the end date of the preceding AE and the start date of the consecutive AE

The presence of at least one SAE / SAE suspected to be study drug related / non SAE has to be checked in a block e.g., among AEs in a  $\leq 1$  day gap block, if at least one SAE is occurring, then one occurrence is calculated for that SAE.

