### 5.1.2 Concomitant medication date imputation

The imputation of a concomitant medication start date will follow the same conventions as for an AE start date (see Section 5.1.2). For concomitant medication reports with no documented end date, medication will be reported as 'ongoing' if captured as such in the eCRF, otherwise it will be reported missing.

No imputation will be performed for concomitant medication end dates.

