##### End date

Imputed date = min (start date of study treatment, last day of the month), if day is missing;

Imputed date = min (start date of study treatment, 31DEC), if month and day are missing.

If the end date is not missing and the imputed start date is after the end date, use the end date as the imputed start date.

If both the start date and the end date are imputed and if the imputed start date is after the imputed end date, use the imputed end date as the imputation for the start date.

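### SAP 5.1.1 imputes an uncertain AE start to the day after dosing without consulting a known end date, so an AE that ended before first dose is counted as treatment-emergent

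*SAP*

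**What the plan says.** Table 5-1 in SAP 5.1.1 sorts partial AE start dates into cases (A) to (E). Its only AE inputs are given in the footnote: "AEM=Month AE started, AEY=Year AE started". These are compared with the month and year of first treatment. Table 5-2 then gives the imputed date. Case (B) is set to TRTSDT+1, the day after first dose, and its legend reads "Uncertain: Partial date insufficient to determine relationship of AE start date to treatment start date". The only text on end dates in 5.1.1 concerns reporting events as ongoing and not imputing missing end dates.

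SAP 2.7 states that "summary tables for AEs will summarize treatment-emergent AEs (i.e. with a start date on or after the first treatment" date. SAP 2.1.1, under the on-treatment definition, starts the on-treatment period on study day 1. It assigns records with incomplete dates to that period only where they cannot be clearly placed before or after dosing.

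A cap at a known end date does appear in the SAP, under 5.1.2.1 for prior therapies: "If the end date is not missing and the imputed start date is after the end date, use the end date" as the imputed start. It is not repeated for AEs. Nor is it repeated in 5.1.2, where "The imputation of a concomitant medication start date will follow the same conventions as for an AE start date".

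**The concern.** A complete end date before first dose settles the question that case (B) treats as open: the event began and finished before treatment. The rule discards that information, gives a start later than the end, and moves a pre-dose event into the treatment-emergent summaries. It also conflicts with SAP 2.1.1, under which such a record can be clearly assigned to the pre-treatment period.

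Such records are possible. Protocol 8.6.1 collects AEs from informed consent, and Protocol 8.6.5 exempts no disease-related event from being an AE. A complaint that starts and resolves between consent and first dose is therefore recorded as an AE. What is at stake is the accuracy of the AE tables and of the registry tables in SAP 2.7.1.1. No efficacy result depends on it.

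**Working it through.** The plan gives no figure to reproduce. The check applies the two tables as written.

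**Inputs.** Case definitions from Table 5-1; imputed dates from Table 5-2; treatment-emergent if the start date is on or after TRTSDT (SAP 2.7 and 2.1.1); the cap from SAP 5.1.2.1.

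**Formulas.** As written, case (B): start = TRTSDT + 1. With the cap: start = min(imputed start, end date).

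**Example.** First dose on 15 Mar 2024, AE start recorded as Mar 2024, so case (B).

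| Known end | Start as written | After end? | Treatment-emergent? | Start with cap | Treatment-emergent with cap? |
|---|---|---|---|---|---|
| 14 Mar | 16 Mar | yes | yes | 14 Mar | no |
| 15 Mar | 16 Mar | yes | yes | 15 Mar | yes |
| 16 Mar | 16 Mar | no | yes | 16 Mar | yes |

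Only the first row is a misclassification. In the second row the start-after-end is impossible, but the status is the same with and without the cap because study day 1 is on-treatment.

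**All cases.** The tables were applied to every dosing date in 2024, with true starts from 20 days before to 40 days after dosing, durations of 0 to 20 days, and either the day or the day and month missing. The grid shows where the rule fails. It does not estimate how often.

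| Case | End relative to first dose | Start after end, as written | Of these, treatment-emergent as written | Start after end with cap |
|---|---|---|---|---|
| (B) | before | 116,410 of 116,410 | 116,410 | 0 |
| (B) | same day | 12,642 of 12,642 | 12,642 | 0 |
| (B) | after | 0 of 540,071 | 0 | 0 |
| (C) | before | 185 of 34,440 | 0 | 0 |

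With the cap, treatment-emergent status falls from 116,410 to 0 in the first row and stays at 12,642 in the second. Cases (A), (D) and (E) gave no start after end in the grid. The date for case (A), "MAX(01MMMYYYY, TRTSDT+1"), has no cap either, but its start month already lies after dosing.

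Case (C) fails through its mid-month default. With first dose on 1 Jun, a start recorded as May and an end of 13 May, the imputed start is 15 May. That is after the end but still before dosing, so the status is unaffected.

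**Size per patient.** One patient wrongly added to a preferred-term row:
- arm of 30 (Table 3-5): 1/30 = 3.3 percentage points
- arm of 40 (Cohort C2, SoC): 1/40 = 2.5 points
- arm of 80 (Cohort C2, combination): 1/80 = 1.25 points

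These are maxima. SAP 2.7.1 counts patients, so someone who also has the term after dosing adds nothing.

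**The case against.** The strongest reply is that SAP 2.1.1 already protects these records: with a complete pre-dose end date, clear assignment is possible and the on-treatment default does not apply. This shows what the authors probably intended, but it does not remove the problem. Table 5-2 judges uncertainty from the partial start date alone, and a programmer following it produces a post-dose start that SAP 2.7 then counts. The two sections conflict for these records and neither is given precedence.

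The second reply is rarity, and it stands. An affected AE must begin after consent, end on a date before the dosing date, lack a start day and have a known end day. Conditions present at consent go to medical history (Protocol 8.6.1), and patients are randomized at the screening visit (Protocol 6.1.2). If consent and dosing fall on the same date, no AE can qualify. Protocol 10.1.5.2 also provides for queries on discrepancies and missing values.

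A reader might infer more than the documents support, in three ways:
- **Events ending on the dosing day are misclassified too.** They are not. They remain treatment-emergent under the date-based definition after the cap; only the impossible date is repaired.
- **Concomitant-medication results are distorted.** Drugs stopped before first dose are prior medications (SAP 2.4.2) and already capped. A drug last given on the dosing day can get a start after its stop, but the summaries in 2.4.2 are by ATC class and drug name, and no visible output uses duration.
- **The registry gap rule fails in general.** The rule ("a single occurrence will be counted if there is" at most a one-day gap) compares one event's end with the next event's start. It matters only when a patient has two AEs with the same SOC and preferred term. An extra occurrence there would be the same false event carried forward, not a separate fault.

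**Conclusion.** The point holds for AEs with a partial start date in case (B) and a complete end date before first dose. Every such record gets a start after its own end and meets the SAP 2.7 definition of treatment-emergent, against the sense of SAP 2.1.1. For AEs ending on the dosing day, and for some case (C) records, the rule gives an impossible date without changing treatment-emergent status.

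The effect is small. Few records are expected, and no frequency can be given because the length of the screening window is blacked out. Each affected patient adds at most 3.3 percentage points to a row in a 30-patient arm. Neither a changed efficacy conclusion nor a changed safety conclusion has been shown.

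This rests on two assumptions. The first is that some patients consent on a calendar date before dosing. The second is that AE collection from consent, taken from the supplied June 2023 protocol amendment, still applies in the March 2024 version on which the SAP is based. The visible text of SAP 5.1.1 shows no redaction, so the missing cap is not an artefact of blacked-out text.

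**What to change.** Add to SAP 5.1.1 the safeguard already in 5.1.2.1: where the AE end date is complete and the imputed start date falls after it, the end date becomes the imputed start date. Repeat it in 5.1.2 so that concomitant-medication dates stay consistent. Add a second sentence stating that an AE with a known end date before first dose belongs to the pre-treatment period, so that 5.1.1 and 2.1.1 agree.

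Records with a missing or partial end date keep the present conservative default, and case (B) events that end after dosing are unchanged. The cost is two sentences for AEs, with the cap repeated in 5.1.2, and a one-line cap in the date derivation. SAP Section 1 already provides for such a change by amendment before database lock.

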### 5.1.2 Concomitant medication date imputation

The imputation of a concomitant medication start date will follow the same conventions as for an AE start date (see Section 5.1.2). For concomitant medication reports with no documented end date, medication will be reported as 'ongoing' if captured as such in the eCRF, otherwise it will be reported missing.

No imputation will be performed for concomitant medication end dates.

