6.8.3 Rescue medication

The following rescue medications may be used per investigator discretion:

- Coartem (Artemether-Lumefantrine)
or
- Other local standard anti-malarial agent

In Part A, Coartem (artemether-lumefantrine) or other local standard anti-malarial agent per investigator discretion will be administered on Day 29 in all patients in Part A of the study. If Coartem or other local standard anti-malarial agent is used as rescue medication prior to Day 29 due to treatment failure (see [Section 8.3.4](#)), then another course is not needed at Day 29.

In Part B, Coartem or other local standard anti-malarial agent per investigator discretion will be used as rescue medication only for patients not randomized to the SoC in Part B if they meet the treatment failure criteria (see [Section 8.3.4](#)). An alternative rescue medication should be used for patients assigned to the SoC arm if they met treatment failure criteria.

Although the use of the above rescue medication is allowable at any time during the study when there is treatment failure in Part A or B, the use of rescue medication should be used at the discretion of the PI following the failure criteria as outlined in [Section 8.3.4](#). The date and time of rescue medication administration as well as the name and dosage regimen of the rescue medication must be recorded.

7 Discontinuation of study treatment and participant discontinuation/withdrawal

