### 1.2.3 Other secondary estimand

CCI

The other secondary estimand is described by the following attributes:

1. **Population:** Adult (Part A)/Adult or adolescent (Part B)/Pediatric (Part C) patients with acute uncomplicated *P. falciparum* malaria.

2. **Variable:** A binary outcome indicating the patient did not take concomitant medication with anti-malarial activity prior to Day 29 and has achieved uncorrected ACPR at Day 29.
3. **Treatment of interest:** anti-malarial agent administered as monotherapy (Part A)/in combination with other anti-malarial agents or SoC (Parts B and C) regardless of study discontinuation or non-compliance.
4. **CCI**
5. **Summary measure:** Uncorrected ACPR rate by treatment group (Part A)/difference in proportion between the combination therapy and SoC (Parts B and C).

The estimand strategy for this estimand is a mixture of treatment policy (for discontinuation or non-compliance) and composite strategy (for non-study anti-malarial agents).

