#### Study day

Study day 1 for all assessments is taken to be the start of study treatment.

The study day for all assessments will be calculated as follows:

1. If date of assessment occurred on or after the start of study treatment, then  
 $\text{Study day} = \text{Date of assessment} - \text{Start of study treatment} + 1.$
2. If date of assessment occurred before the start of study treatment, then  
 $\text{Study day} = \text{Date of assessment} - \text{Start of study treatment}.$

The study day will be displayed in the data listings. If an event starts before the reference start date, the study day displayed on the listing will be negative.

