### **2.4.2 Prior, concomitant and post therapies**

Prior medications are defined as drugs taken and stopped prior to first dose of study treatment. Any medication given at least once between the day of first dose of study treatment and the last day of study will be a concomitant medication, including those which were started pre-baseline and continued into the treatment period.

Prior and concomitant medications will be coded according to the latest version of WHO Drug Reference List dictionary which employs ATC.

The following will be summarized separately by ATC grade and preferred drug name: (1) prior medications, (2) concomitant medications, and (3) non-study anti-malarial drugs ([Table 5-6](#)). The Safety set will be used.

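### The AE date rule also covers non-study antimalarials, so a partial start date from Day 29 or later would usually be placed before Day 29; these drugs need their own rule

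*SAP*

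**What the plan says.** **Rule.** SAP 5.1.2 states: "The imputation of a concomitant medication start date will follow the same conventions as for an AE start date". Its cross-reference for that convention points to 5.1.2 itself; the AE rule is in 5.1.1 (Tables 5-1 and 5-2):

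- Known month after the dosing month: "MAX(01MMMYYYY, TRTSDT+1", that is, the later of the first of that month and the day after dosing.
- Dosing month, or dosing year with the month missing: the day after dosing. This is Day 2, because "Study day 1 for all assessments is taken to be the start of study treatment".
- Later year with the month missing: 1 January of that year.
- Year missing: "Not imputation".

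**Drugs covered.** SAP Table 5-6 takes non-study antimalarials from the concomitant medication dataset, and deviation code COMD02 adds others. No exemption from 5.1.2 is visible. A footnote limits the Part A list to patients who took Coartem before the Day 29 visit.

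**Where timing matters.**

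- SAP 1.2.3, uncorrected ACPR in all parts: "A binary outcome indicating the patient did not take concomitant medication with anti-malarial activity prior to Day 29", combined with response at Day 29 under a composite strategy.
- SAP 2.5.1, Parts B/C primary analysis: use before Day 29 is compatible with the principal stratum only as rescue for recrudescence.
- SAP 2.5.3, Part A primary analysis: use within the first 7 days and before clearance sets PCT to 144 hours.

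**Routine Day 29 course.** Protocol 6.8.3 says that Coartem or another local standard antimalarial "will be administered on Day 29 in all patients in Part A of the study", unless rescue was already given. It also requires date and time to be recorded for rescue medication.

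**Prior therapies.** The end-date rule in SAP 5.1.2.1 reads "Imputed date = min (start date of study treatment, last day of the month), if day is missing", while SAP 2.4.2 says "Prior medications are defined as drugs taken and stopped prior to first dose of study treatment".

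**The concern.** Moving an uncertain date early is a sensible convention for adverse events, because it avoids missing a treatment-emergent event. For an antimalarial the date does a different job: it can decide whether a patient has an intercurrent event before Day 29. An early-date rule can then only create apparent early use; it cannot hide it.

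Part A is the natural place for this to occur, since the plan itself schedules an antimalarial exactly on the cut-off day. The Table 5-6 footnote shows that the SAP means to separate this course from earlier use. But the footnote is itself a date comparison, so an early imputed date would defeat it, and it names only Coartem although another agent is allowed. In Parts B and C the corresponding case is a drug taken after Day 29, for example for a reinfection during follow-up to Day 43.

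**Working it through.** The plan gives no figure on this point to reproduce. The check applies Tables 5-1 and 5-2 to every dosing date in 2023-2026 (1,461 dates, 48 month starts, each date assumed equally likely).

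**1. Worked dates, day missing, month and year known**

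| Dosing (Day 1) | True start | Imputed | Scored before Day 29? |
|---|---|---|---|
| 10 Jan | 7 Feb (Day 29) | 1 Feb = Day 23 | yes |
| 2 Jan | 30 Jan (Day 29) | 3 Jan = Day 2 | yes |
| 10 Jan | 14 Feb (Day 36) | 1 Feb = Day 23 | yes |
| 3 Jun | 1 Jul (Day 29) | 1 Jul = Day 29 | no |

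**2. Share of dosing dates affected.** A true start on Day D (29 to 43) escapes only if the first of its month falls between Day 29 and Day D, that is, if its day of the month is at most D - 28. So:

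share placed before Day 29 = 1 - 48 × (D - 28)/1461

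- Day 29: 1 - 48/1461 = 96.7%
- Day 31: 1 - 144/1461 = 90.1%
- Day 36: 1 - 384/1461 = 73.7%
- Day 43: 1 - 720/1461 = 50.7%
- Days 30-43, equally weighted (mean D - 28 = 8.5): 1 - 408/1461 = 72.1%

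With the month also missing, the share is 99.7% at Day 29 and 95.9% at Day 43. The earliest-day rules in SAP 5.1.2.2 and 5.1.2.3 also give 96.7% at Day 29 with the day missing.

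**3. Direction.** With only the day missing, no true start on Days 2-28 is imputed later than the truth or before treatment. The error runs one way.

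**4. Reach of the PCT rule.** A true Day 29 start is imputed to Day 7 or earlier when its day of the month is 23 or later: (1461 - 22 × 48)/1461 = 405/1461 = 27.7%. This is an upper bound, because the rule also requires that parasites had not yet cleared.

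**5. Effect of one affected success**

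- Uncorrected ACPR (success becomes failure): 1/30 = 3.3 points, 1/40 = 2.5, 1/80 = 1.25. These are the Parts B/C arm sizes in SAP Tables 3-5 and 3-7; no Part A arm size is visible.
- Parts B/C primary analysis (success excluded): 29/30 = 96.7% becomes 28/29 = 96.6%, about 0.1 point.

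**6. Frequency of partial dates.** Not given. As an assumption only, if a share p of Part A Day 29 courses had the day missing after queries, p × 0.967 of those patients would be misplaced: none at p = 0, 1.0% at p = 1%, 4.8% at p = 5%.

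**7. Would a latest-day rule be better?** Using the last day of the known month, a true Day 29 start is never placed before Day 29. But a true start on Day D < 29 is placed at Day 29 or later with share 1 - 48 × (29 - D)/1461: 31% at Day 8, 54% at Day 15, 77% at Day 22, 97% at Day 28. A fixed late rule only moves the error.

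**The case against.** The strongest objection is that the link to the endpoints is inferred. No visible text says that imputed dates enter ACPR, stratum membership or PCT. Most of the responder rules (SAP 2.1.2.1), the Parts B/C intercurrent-event list (2.5.3) and Table 5-9 are blacked out, and 2.5.4 sends missing ACPR values to Table 5-9. A reader might infer that the imputed date does decide responder status; the documents do not support that as fact. The conditional form stands, because the definitions need a date and 5.1.2 is the only visible rule that supplies one.

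Second, the trigger should be uncommon. The Part A course falls on a study visit, rescue medication needs date and time (Protocol 6.8.3), and missing values are queried (Protocol 10.1.5.2). A reader might take 96.7% for an error rate. It is not: it applies only once a date is partial.

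Third, it is tempting to attach 3.3 points to Part A or to the primary endpoint. Neither follows: the figure uses a Parts B/C arm size and the secondary uncorrected ACPR. Likewise, 27.7% is not the share of Part A patients whose PCT would be reset.

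Fourth, the earliest date is a defensible conservative choice within one arm, particularly for self-medication between visits, the most realistic source of partial dates. That stands, and the fix keeps it as the default. It need not be conservative for the difference from SoC if partial dates are more frequent on SoC.

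**Conclusion.** The concern holds in conditional form, as a cheap improvement. The AE start-date rule governs partial dates of non-study antimalarials with no visible exception. If those dates feed the endpoints, a true start on or after Day 29 with the day missing is usually placed before Day 29, and the error never runs the other way. The consequence is a false failure on uncorrected ACPR in any part, or an exclusion from the Parts B/C principal stratum that barely moves the rate.

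This rests on three assumptions: the blacked-out rules do not already deal with it; dosing dates are spread evenly over the calendar; and the routine Part A Day 29 course still applies. On the last, the SAP cites protocol version 03 of March 2024, whereas the protocol supplied is Amendment 2 of June 2023; the Table 5-6 footnote suggests that the course was kept. The number of patients affected cannot be stated.

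The prior-therapy end date is a separate consistency matter. A missing stop day in the dosing month becomes the dosing date, while 5.1.2.1 places the matching uncertain start one day before treatment. A reader might infer that this reclassifies the drug as concomitant. In fact SAP 2.4.2 is ambiguous for a drug stopped on the dosing day before dosing, and no endpoint effect is shown.

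**What to change.** In SAP 5.1.2:

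1. Exempt Table 5-6 and COMD02 drugs from the AE rule whenever they are placed relative to Day 29 or Day 7.
2. After query, if the partial date is compatible with a visit at which failure, reinfection or (Part A, with no earlier failure or rescue recorded) the routine Day 29 course is documented, use that visit date.
3. Otherwise keep the earliest possible date for the main analysis and report the latest possible date as a sensitivity analysis.
4. Apply the same exception to 5.1.2.2 and 5.1.2.3, and correct the cross-reference from 5.1.2 to 5.1.1.

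If Table 5-9 already contains such a rule, a sentence in 5.1.2 pointing to it is enough.

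As a minor edit, change the prior-therapy end-date rule to the minimum of treatment start minus 1 and the last day of the month, and likewise for 31 December.

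The cost is SAP wording and a few lines of derivation code. The downside is that a truly early but undated drug could be assigned to a visit date; an earliest-date sensitivity run for the visit-anchored records covers that.
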